### 11.7 Anticipated or Unanticipated

If an AE is determined to be related to the study device the sponsor will then assess the event to determine if it is anticipated or unanticipated.

- **Anticipated:** the event is identified in the CIP; labeling; report of priors or user quide.
- Unanticipated: the event has not been previously identified in the CIP; labeling; report of priors or user guide.

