### **Study Stopping Rules**

The study may be stopped if the Data Monitoring Committee (DMC) determines that there are significant safety issues, including the occurrence of certain types of individual adverse events (i.e. UADE, device related DKA, and device related Severe Hypoglycemia) that have undergone expedited adjudication by the Clinical Events Committee (CEC). See CEC Section 12.1 and DMC Section 12.2 for more details regarding the expedited review responsibilities of both committees.

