### Risks with use of Lyumjev:

- Hyperglycemia or hypoglycemia
- Hypokalemia
- Hypersensitivity reactions
- Injection/infusion site reaction
- Allergic reaction
- Rash
- Pruritus
- Lipodystrophy
- Weight Gain

[figure not shown]

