#### 11.2 Definitions and Classification of Adverse Events

Medtronic uses the definitions provided in ISO 14155:2020 and 21 CFR 812 for AE definitions. Where the definition indicates "device", it refers to any device used in the study. This might be the device under investigation, or any market released component of the system.

Severe Hypoglycemia is an event requiring assistance of another person due to altered consciousness to actively administer carbohydrate, glucagon, or other resuscitative actions.

This means that the subject was impaired cognitively to the point that he/she was unable to treat himself or herself, was unable to verbalize his or her needs, and was incoherent, disoriented and/or combative.

These episodes may be associated with sufficient neuroglycopenia to induce seizure or coma. Plasma glucose measurements may not be available during such an event, but neurological recovery attributable to the restoration of plasma glucose to normal is considered sufficient evidence that the event was induced by a low plasma glucose concentration.

**Severe Hyperglycemia** is defined as hyperglycemia (BG greater than [>] 300 mg/dL or 16.7 mmol/L) with BG ketones greater than (>) 1.5 mmol/L, and/or accompanied by symptoms of nausea, vomiting or abdominal pain.

The meter and ketone test strips are supplied for the evaluation of ketone monitoring. Only blood ketones will be recognized (not urine ketones) for assisting in diagnosis of severe hyperglycemia. The

monitors/test strips are quality controlled prior to dispensing to subjects. Blood ketones provide contemporaneous understanding of ketone levels associated with elevations in glucose.

**Diabetic Ketoacidosis/DKA diagnostic criteria**: BG greater than (>) 250 mg/dL or greater than (>) 13.9 mmol/L, arterial pH less than (<) 7.3, bicarbonate less than (<) 15 mEq/L, moderate ketonuria or ketonemia and requiring treatment within a health care facility.

Hyperglycemic events will be recorded as DKA if the event includes the presence of all of the following:

- Arterial blood pH less than (<) 7.30 or serum bicarbonate less than (<) 15 mEq/L
- Blood glucose greater than (>) 250 mg/dL or greater than (>) 13.9 mmol/L
- Serum ketones or large/moderate urine ketones
- Symptoms such as polyuria, polydipsia, nausea, or vomiting
- Treatment provided in a health care facility

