#### **Unanticipated Adverse Device Effect (UADE) (21 CFR 812.3(s))**

Any serious adverse effect on health or safety or any life-threatening problem or death caused by, or associated with, a device, if that effect, problem, or death was not previously identified in nature, severity, or degree of incidence in the investigational plan or application (including a supplementary plan or application), or any other unanticipated serious problem associated with a device that relates to the rights, safety, or welfare of subjects.

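### Section 11.7 calls a device-related event anticipated on listing alone, which conflicts with the UADE definition in Section 11.2 and may under-classify listed harms that prove worse or more frequent than described

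*Protocol*

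**What the plan says.** Section 11.7 of the Protocol applies once an adverse event has been judged related to the study device: "the sponsor will then assess the event to determine if it is anticipated or unanticipated". The event is anticipated if "the event is identified in the CIP; labeling; report of priors or user quide". It is unanticipated if "the event has not been previously identified in the CIP; labeling; report of priors or user guide". Neither half mentions severity or frequency.

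Section 11.2 states that "Medtronic uses the definitions provided in ISO 14155:2020 and 21 CFR 812 for AE definitions". Its UADE entry, taken from 21 CFR 812.3(s), covers a serious effect associated with a device that "was not previously identified in nature, severity, or degree of incidence in the investigational plan or application".

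UADE status has consequences elsewhere in the Protocol:

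- Section 11.5: the investigator reports a UADE to the sponsor and IRB within 10 working days.
- Section 12.1: the CEC adjudicates UADEs, device-related DKA and device-related severe hypoglycemia within 10 days of sponsor notification.
- Section 12.2: the DMC meets within 10 days of the CEC adjudicating one of those three.
- Study Stopping Rules: the individual events named are the same three ("i.e. UADE, device related DKA, and device related Severe Hypoglycemia").

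**The concern.** The rule that the sponsor is told to apply event by event is narrower than the definition it should serve. Under 11.7 the only question is whether the harm's name appears in one of four sources. Under 11.2 a named harm can still be unanticipated if its severity or its frequency was not described.

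The Protocol's own risk tables in Section 10.1 name many harms, almost all without a grade or an expected rate. Examples are allergic reaction and infection under both sensors and transmitter, and coma, shock, cardiovascular event and death under hyperglycemia or hypoglycemia. Listing in the Protocol is enough for 11.7, so a literal reading makes a broad range of serious device effects anticipated whatever the data show.

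Device-related DKA and device-related severe hypoglycemia are protected, because they are expedited by name. For other serious device effects, such as an allergic reaction to a sensor or device-related severe hyperglycemia, UADE status is the only route that carries the 10-day deadlines. A misclassification there delays the committees' formal look at the event.

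**Working it through.** No arithmetic reproduces or refutes this point, since it concerns a classification rule. The check sets the passages side by side.

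**1. The two tests.**

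| | Section 11.7 | Section 11.2 (UADE) |
|---|---|---|
| Applies to | any device-related AE | serious device effects |
| Criterion | named or not named | nature, severity, degree of incidence |
| Sources | Protocol, labeling, report of priors, user guide | investigational plan or application, with supplements |
| Who is named as deciding | sponsor | not stated |

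The criteria differ, and so do the sources: 11.7 adds labeling and the user guide, and 11.2 adds the application. No passage gives an order of precedence.

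**2. Where they disagree.** Take a serious device-related event whose name appears in Section 10.1.

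- *Severity.* Allergic reaction is listed as a sensor risk with no grade. Suppose one is far more severe than anything described. Read literally, 11.7 returns anticipated. Section 11.2 can return UADE, because that severity was not identified.
- *Incidence.* Hyperglycemia secondary to infusion set occlusion is listed with no rate. Suppose serious cases occur well above what was described. Section 11.7 again returns anticipated, while 11.2 can return UADE.

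For an event not named in any source, both tests point to unanticipated. The conflict is confined to named harms that exceed their description.

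**3. What follows from the label.** With UADE status, the stated steps are CEC within 10 days of sponsor notification, then DMC within 10 days of adjudication, so 10 + 10 = 20 days to a DMC meeting (Section 12.1 allows final disposition to be delayed while information is obtained). Without it, the scheduled DMC meeting is about every 90 days, so an event just after one meeting could wait up to about 90 days for the next unless an ad hoc meeting is called. The difference is up to about 90 − 20 = 70 days. This is a calendar bound from the Protocol's own intervals, not an estimate of typical delay. A subject's study period is itself about 90 days (Visit 15 at Day 90, +7 days).

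**4. Whether another rule supplies the missing deadline.**

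- Section 11.4 asks for SAEs and SADEs to reach the sponsor as soon as possible, ideally within 24 hours. That informs the sponsor, who then applies 11.7.
- Section 12.1 has the CEC review all SAEs, SADEs and severe hyperglycemia, but the 10-day clock covers only the three named categories. Reconsidering whether an event was unanticipated is optional. The required task is agreement with the investigator's classification, whereas 11.7 assigns this one to the sponsor.
- Section 12.2 has the DMC follow rates of all SAEs and of device-related AEs. Table 5 gives reference rates only for severe hyperglycemia (71.64 per 100 patient years, under 15 years only), DKA and severe hypoglycemia. No rate is stated that would trigger an ad hoc meeting.

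**The case against.** The strongest reply is that 11.7 does not define UADEs at all. It never uses the term and does not claim to replace 11.2, which adopts the regulatory definition in full. An event that meets 11.2 is a UADE whatever label 11.7 gives it, and Section 11.5 obliges the investigator to report it with no 11.7 step in between. This stands as a reading of the text, and it rules out any claim that a listed harm cannot become a UADE. It does not remove the conflict: the sponsor has two written tests, and nothing says which to use.

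The second reply is that serious events are reviewed anyway: by the CEC, by the DMC on schedule or ad hoc, and under a stopping rule whose list is introduced as examples of significant safety issues rather than as a closed set. This also stands. It reduces the consequence from loss of review to loss of a deadline.

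The third reply concerns examples. "Injection/infusion site reaction" is listed as a risk of the insulin, and 11.7 covers device-related events only, so a reaction attributed to the insulin alone would not be reached by changing it. Section 11.2 already describes site reactions up to ulceration or necrosis, and Section 11.3 gives hospitalized cellulitis at an insertion site as an example of a serious device effect. For these, the severity part of 11.2 would often agree with 11.7. The point therefore should not rest on infusion-site harms.

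Finally, the labeling, report of priors and user guides are not among the documents. They may state severities or rates, so how often the two tests would diverge cannot be checked here.

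**Conclusion.** The inconsistency is real and should be corrected. Section 11.7 is a stated rule that can give a different answer from 11.2, and the answer decides whether the 10-day CEC and DMC steps apply. It affects serious, named, device-related effects, other than DKA and severe hypoglycemia, that turn out worse or more frequent than described. The consequence is possible under-classification and a later committee review. No endpoint, hypothesis test, sample size or power figure depends on it.

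A reader might infer that a listed harm can never become a UADE or reach expedited review, or that the chance of flagging an excess is zero. The documents do not support either. Section 11.2 still defines such an event as a UADE, the CEC may revisit the question, the DMC can meet ad hoc, and two event types are expedited regardless of listing. A zero probability would only restate one literal reading of 11.7 as a number.

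The conclusion assumes that the sponsor applies 11.7 as written and that its label is carried into the decision on UADE status. Confidence is high for the mismatch in wording and lower for its practical effect, since the documents give no count or rate of the events concerned.

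**What to change.** Reconcile the two sections by giving 11.7 the 11.2 test. A device-related event is anticipated only if it was previously identified in nature, severity and degree of incidence; it is unanticipated if any of the three was not. Add one sentence stating that the 11.2 definition governs UADE status, including which source documents count.

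A separate running comparison of event counts with described rates is not needed and would not be workable: the Section 10.1 tables give no rates, Table 5 covers three event types, and review of aggregate rates already sits with the DMC. Where the plan and application describe no rate, the incidence element stays a matter of judgment, and the sponsor should record the basis for it.

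The cost is one or two sentences in Section 11.7. A few more events may enter the 10-day CEC and DMC route. Nothing in the endpoints, the analyses or the SAP has to change.

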#### **Data Review Committees 12**.

#### 12.1 Clinical Events Committee

A clinical events committee (CEC) consisting of external physicians with an expertise in endocrinology and the management of diabetes including insulin pumps and CGM will be convened. The CEC will review AEs as required per protocol, which include reports of:

- Serious adverse event
- Serious adverse device effect
- Unanticipated adverse device effect
- Severe hypoglycemia
- Diabetic ketoacidosis
- Severe hyperalycemia

CEC is to review and adjudicate unanticipated adverse device effects (UADE), device related DKA, and device related severe hypoglycemia within 10 days from the time that the sponsor is notified.

The CEC will assess events to determine agreement or disagreement with the investigator classification of an event.

If the CEC disagrees with the investigator's classification of the event, the rationale will be provided to the investigator. If the investigator agrees with the CEC's adjudication, the CRF documenting the AE will be updated accordingly.

If the investigator does not agree with the CEC's adjudication classification, both determinations will be provided within the final report; however, the CEC's adjudication will be used for data analysis. The disagreement will also be included in reporting to IRBs and regulatory authorities, if required.

The CEC may review applicable information for device related AEs which may include:

- Whether or not the event was unanticipated
- Review of sensor data from CareLink Personal/CareLink system software report (when applicable)
- Review of pump data from CareLink Personal/CareLink system software report (when applicable)
- Misuse of the device by the user

Review of events may require the following information. Final disposition may be delayed based on obtaining this information:

- Monitoring by sponsor at investigational center
- Device return and failure analysis
- CareLink Personal/CareLink system software upload and review of software reports
- Subject clarification to investigational center regarding details about the event
- Source documents that support event: Paramedic records; ER records; Lab records; Hospital admission and discharge summary

The following factors should be carefully considered in the CEC's recommendation to sponsor:

- 1. Was the severe hypoglycemia or DKA related to the AHCL algorithm, or was it related to a known insulin pump risk? For example, a question that may be considered in DKA would be whether the event was related to an infusion set issue or caused by the AHCL algorithm.
- 2. Another important consideration would be if the severe hypoglycemia, severe hyperglycemia or DKA event was related to a device malfunction versus patient non-compliance. For example, if a software anomaly leading to an under-delivery of insulin is discovered versus the subject repeatedly ignoring alarms prompting the subject to take action.
- 3. Severe hypoglycemia, severe hyperglycemia or DKA caused directly by an infusion set issue when the study pump is functioning as intended would likely result in acceptance to proceed with the study versus severe hypoglycemia or DKA that are directly caused by the AHCL algorithm or a device malfunction might stop study enrollment or entire study altogether.
- 4. It should be noted that the final determination of causality related to 780G system that is made by the CEC may include additional factors which the members consider to be clinically relevant and important.

[figure not shown]

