#### 11.6 Causality Assessment

An AE is not automatically related to the study device or procedure simply because the subject is wearing the device and participating in the study. The event should be reviewed to determine if the device or study procedure could have possibly caused the event and therefore is related to the study device or procedure.

[figure not shown]
Causality assessment is the determination of the relationship between an AE and the device being studied. It is expected that the investigational center will review all elements surrounding the AE to properly assess the causality of the event to the study device or to a study procedure. This review would include the subjects' description of the event, study device uploads and medical records (if applicable) from the treating facility. These records will be made available to sponsor. Investigators should classify the relationship between the AE and the study device or study procedures using one of the four possible causality categories listed below:

- **Not related:** relationship to the device, comparator, or procedures can be excluded when:
  - o the event has no temporal relationship with the use of the investigational device or the procedures related to the application of the investigational device;
  - o the event does not follow a known response pattern to the medical device (if the response pattern is previously known) and is biologically implausible;
  - the discontinuation of medical device application or the reduction of the level of activation/exposure - when clinically feasible - and reintroduction of its use (or increase of the level of activation/exposure), do not impact on the event;
  - the event involves a body-site or an organ not expected to be affected by the device or procedure;
  - o the event can be attributed to another cause (e.g., an underlying or concurrent illness/ clinical condition, an effect of another device, drug, treatment or other risk factors);
  - the event does not depend on a false result given by the investigational device used for diagnosis, when applicable;

In order to establish the non-relatedness, not all the criteria listed above might be met at the same time, depending on the type of device/procedures and the event.

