#### The DMC will perform 4 main functions:

**First:** DMC will track and trend the overall safety of the study.

D00409632 Version E Page 87 of 106

Event rate, defined as number of events per 100 patient years, will be reviewed by the DMC with respect to the following:

- Event rate of all SAEs
- Event rate of severe hypoglycemia
- Event rate of severe hyperglycemia
- Event rate of DKA
- Event rate of device related AEs

Second: Based on their meetings, DMC will recommend a decision to the sponsor regarding the followina:

- Whether or not enrollment should be halted.
- Whether or not the entire study will need to be stopped including for those subjects who have received study devices already.

Note: If it is decided to withdraw subjects from participation in the study or if the study is stopped, subjects will be followed-up in accordance with standard practice by their own providers.

**Third:** During the study, the following steps will be taken for:

- Unanticipated adverse device effects (UADE)
- Device related DKA
- Device related severe hypoglycemia

DMC is to meet within 10 days from the time that the CEC adjudicates an event as one of the above. If possible, the investigator should be available to answer questions by DMC.

Based on their meetings, DMC will recommend a decision to the sponsor regarding the following:

- Whether or not enrollment should be halted.
- Whether or not the entire study will need to be stopped including for those subjects who have received study devices already.

Note: If it is decided to withdraw subjects from participation in the study or if the study is stopped, subjects will be followed-up in accordance with standard practice by their own providers.

Fourth: The DMC will review Safety data and provide a recommendation to the sponsor regarding staged enrollment of pediatric subjects:

The DMC will provide a recommendation to proceed with the following staged enrollment:

Enrollment of pediatric subjects 7-17 years of age into the study may not proceed until N=10 subjects 18 years of age or older have completed 30 days of the study period and the Data Monitoring Committee (DMC) has determined it is safe for subjects 7-17 years of age to be enrolled in the study.

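### The CEC's 10-day limit covers UADEs and only those DKA and severe hypoglycemia events that are device related; one the site codes as not related has no adjudication deadline

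*Protocol*

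**What the plan says.** Four parts of the protocol define the pathway. The SAP sets no CEC timeline.

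- **Scope of CEC review (12.1).** "The CEC will review AEs as required per protocol, which include reports of" serious adverse events, serious and unanticipated adverse device effects, severe hypoglycemia, DKA and severe hyperglycemia. This list is not restricted by relatedness and carries no time limit.
- **CEC deadline (12.1).** UADEs are to be reviewed and adjudicated on a fixed clock, together with "device related DKA, and device related severe hypoglycemia within 10 days from the time that the sponsor is notified". The same section lists records and device analyses that a review may need and adds: "Final disposition may be delayed based on obtaining this information".
- **Who classifies first (11.6, 12.1).** "Investigators should classify the relationship between the AE and the study device or study procedures using one of the four possible causality categories listed below"; one of the four is 'Not related'. The CEC comes second: "The CEC will assess events to determine agreement or disagreement with the investigator classification of an event".
- **DMC trigger (12.2, third function).** For UADEs, device-related DKA and device-related severe hypoglycemia, "DMC is to meet within 10 days from the time that the CEC adjudicates an event as one of the above".

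Section 9.9 names the same three event types among the safety issues on which the DMC may stop the study, describing them as events "that have undergone expedited adjudication by the Clinical Events Committee (CEC".

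**The concern.** Section 12.1 uses relatedness as the entry condition for fast adjudication, and relatedness is the judgment that adjudication is meant to verify. A correctly coded device-related event moves quickly. A device-related event that the site has miscoded as not related waits in the general review list with no date attached, although an independent second opinion matters most there.

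Miscoding is plausible. The only worked causality example in 11.6 concerns severe hyperglycemia and turns on infusion-set findings: glucose that improves without a set or site change is coded as not related. An event driven by the control algorithm need not show any infusion-set sign. Yet 12.1 tells the CEC that algorithm-caused events are the kind that might stop enrollment or the study.

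The expedited DMC meeting is at stake, because its clock starts from the CEC's ruling. The DMC also decides when pediatric enrollment may open, after 10 adults have completed 30 days of the study period. Neither 12.1 nor 12.2 requires an adult DKA or severe hypoglycemia coded as not related to be adjudicated before that decision.

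**Working it through.** No sample size, power or error rate is involved. The check sets the stated clocks side by side and then gauges the workload of a change.

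**1. Event coded by the site as possibly, probably or causally related**

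- Sponsor notification to CEC adjudication: 10 days (12.1).
- CEC adjudication as device related to DMC meeting: 10 days (12.2).
- Notification to DMC meeting: 10 + 10 = 20 days.
- DMC recommendation, in general within 1 week of the meeting (12.2): 20 + 7 = 27 days.

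The 20 days is a nominal limit, because 12.1 allows final disposition to be delayed.

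**2. Event coded by the site as not related**

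- Sponsor notification to CEC adjudication: no figure in either document.
- If the CEC reclassifies it as device related, DMC meeting: 10 days after that ruling.
- Notification to DMC meeting: (unspecified) + 10 days, so no upper bound.
- If the CEC agrees that it is not related, no expedited DMC meeting is due.

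**3. Whose classification starts the CEC clock**

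Section 12.1 does not say. The clock starts at sponsor notification. The only relatedness call that the protocol provides by then is the investigator's (11.6), and the CEC's comes at the end of the interval being timed. That the site's code governs is therefore an inference, though a strong one.

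**4. Other provisions that could supply a deadline**

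| Provision | What it does | Sets a CEC deadline? |
|---|---|---|
| 11.4 | All severe hypoglycemia and DKA reported to the sponsor as soon as possible, 24 hours desired, whatever the relatedness | No |
| 11.6 | Relatedness that cannot be assessed is coded as possible | No; does not reach an event positively coded as not related |
| 12.2, first function | DMC sees overall severe hypoglycemia and DKA rates | No |
| 12.2 | DMC meets about every 90 days and ad hoc | No; no ad hoc trigger is given for these events |

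**5. Number of events a wider clock would cover**

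Inputs:

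- 200 subjects entering the study period (8.1).
- 90 days of study period (Visit 15) plus about 21 days of run-in (Visit 6 at day 14, Visit 7 up to 7 days later).
- Reference rates per 100 patient-years from Table 5 in 12.2.

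Exposure = 200 × (90 + 21) / 365.25 = 60.8 patient-years. This assumes full follow-up and ignores subjects who leave during run-in.

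- Severe hypoglycemia at 20.9, the highest rate listed: 60.8 × 0.209 = 12.7.
- DKA at 3.6, the highest clinical-trial rate: 60.8 × 0.036 = 2.2.
- DKA at 9.9, the registry rate in youth: 60.8 × 0.099 = 6.0.

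Table 5 also contains rates of 0 for both events, so the ranges are about 0 to 13 severe hypoglycemia and 0 to 6 DKA. Applying the highest rate to all ages overstates the load. The share that sites would code as not related is not given.

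**The case against.** The strongest defense is that this is deliberate triage: events already flagged as device related go first. The coding rules make 'Not related' a narrow category, since weak links that cannot be ruled out and unassessable cases both go to 'Possible', and 11.2 counts any device used in the study. The sponsor hears of every such event quickly, the CEC must review it in any case, and the DMC can meet ad hoc. All of this stands and keeps the gap small. None of it gives a date by which the CEC must rule on an event the site has positively coded as not related.

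Three stronger readings are tempting, and the documents do not support them:

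- *A reclassified event falls outside the stopping rule.* A reader might infer this from the expedited-adjudication phrase in 9.9. But that section introduces these events as examples of significant safety issues, not as a closed list. The 12.2 meeting trigger depends on the CEC's ruling, however that ruling was reached, and the second DMC function allows a recommendation to halt or stop from its meetings. No stopping power is lost.
- *The expedited DMC review may never happen.* CEC review is mandatory and reclassification starts the DMC clock. The review would be lost only if the ruling came too late to be of use, for example after the study had ended.
- *The delay is about 70 days (90 − 20), with a corresponding block of extra patient exposure.* The 90 days is the routine DMC interval. The missing figure is the CEC's adjudication time, for which the documents give neither a value nor a bound. An exposure figure would also need an accrual pattern that they do not give, and would have to ignore ad hoc meetings.

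A fair practical objection is that 10 days may be too short when a review needs hospital records or device failure analysis. That is a real cost of the change and is allowed for in it.

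**Conclusion.** The concern holds as a gap in the adjudication timeline. DKA and severe hypoglycemia coded by the site as not related must be reviewed by the CEC but have no adjudication deadline. If the CEC reclassifies one as device related, the DMC meeting can therefore come later, by an amount the protocol does not bound, than the nominal 20 days that apply otherwise.

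This rests on one inference, that the investigator's code decides which events enter the 10-day clock. If the sponsor intends something else, 12.1 needs to say so. How often the gap would matter cannot be estimated, because the documents do not give the miscoding rate. The other safeguards limit its practical effect, and the DMC's general authority under 9.9 is intact. It is a cheap improvement to safety oversight and does not affect the endpoints or their analysis.

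**What to change.** In 12.1, replace the sentence that sets the deadline with wording to this effect:

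*The CEC reviews and adjudicates every UADE, every DKA and every severe hypoglycemia within 10 days of sponsor notification, whatever relatedness the investigator assigned. Where records or device analysis are still pending, final disposition may follow later, as already provided in this section.*

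This also settles whose classification starts the clock, since none would be needed. The DMC trigger in 12.2 can stay as it is: an event reclassified within the 10 days would reach a DMC meeting by day 20 and a recommendation by about day 27. Changing 9.9 to refer simply to adjudicated events would be optional tidying.

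Cost: one sentence of protocol text and no added CEC reviews, since all these events are reviewed already. Initial review of every such event would fall under the 10-day limit, at the higher Table 5 rates about 13 severe hypoglycemia and 2 to 6 DKA events in total, some of them on the clock already. Some of those deadlines may be hard to meet, which is why the allowance for delayed final disposition should be kept.
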